
6.6.1.3. Endometrial Biopsy

Per the parent study MVT-601-3001 protocol, an endometrial biopsy is performed for all subjects at the Week 24 visit, whereas per the parent study MVT-601-3002 protocol, an endometrial biopsy is performed at the Week 24 visit only if indicated (endometrial thickness at any location is ≥ 4 mm or if any other endometrial abnormality is visualized on the Week 24 ultrasound). If the required Week 24 biopsy is inadequate for diagnosis, it should be repeated, and a sample submitted to the central laboratory. If the second sample is inadequate, ensure an endometrial thickness has been reported from the Week 24 transvaginal ultrasound and contact the medical monitor to review the findings. Patients who have endometrial hyperplasia or endometrial carcinoma, will be withdrawn from study drug treatment and followed per instructions in the parent study protocol.

Additional assessment of the effects of relugolix co-administered with low-dose estradiol and norethindrone acetate on the endometrium will be performed at Week 52 and submitted to the central laboratory. If the Week 52 biopsy specimen is inadequate, the endometrial thickness reported at the Week 52 transvaginal ultrasound will be used to determine if further action is required:

- Endometrial thickness ≤ 5 mm – no further action required.
- Endometrial thickness > 5 mm at any location or any other endometrial abnormality – repeat endometrial sampling. Contact medical monitor if second specimen is inadequate for diagnosis.

Patients who decline endometrial sampling at Week 52 will not be prohibited from participating in the randomized withdrawal study.

Unscheduled endometrial biopsies may also be performed when medically indicated and as deemed necessary by the investigator. The investigator should obtain approval from the sponsor to perform an unscheduled endometrial biopsy, unless urgently indicated. Additional consent is not required in this circumstance.

6.6.1.4. Pharmacodynamics Sample Collection

Blood samples for the pharmacodynamic analysis of serum estradiol will be collected pre-dose at the visits indicated in the study Schedule of Activities (see Section 1.1). These pharmacodynamic samples will be analyzed at a central laboratory.

6.6.1.5. Menorrhagia Impact Questionnaire

The Menorrhagia Impact Questionnaire was designed to measure a women's self-assessment of menstrual blood loss and its impact on her social and leisure activities, physical activities, and ability to work (see [Appendix 1](#)). The MIQ has undergone psychometric validation. Patients will complete the MIQ at each study visit during the Open-Label Treatment period. Patients will complete the MIQ at each visit at the site before other study procedures, such as blood draws and physical examinations, are performed.

6.6.1.6. Uterine Fibroid Symptom – Quality of Life

The Uterine Fibroid Symptom and Health-Related Quality of Life score is used to evaluate the symptom severity and the quality of life of patients with uterine fibroids (see [Appendix 1](#)). Patients will complete the UFS-QoL questionnaire at the site at the Week 24/Baseline visit, Week 36, and Week 52/Early Termination visit before other study procedures, such as blood draws and physical examinations, are performed.

6.6.1.7. European Quality of Life Five-Dimension Five-Level Scale

The European Quality of Life Five-Dimension Five-Level Scale is a standardized instrument for use as a measure of health outcomes (see [Appendix 2](#)). Mobility, self-care, usual activities, pain/discomfort, and anxiety/depression are each assessed on 5-point categorical scales ranging from “no problem” to “severe problem.”

Patients will complete the EQ-5D-5L questionnaire at the site at the Week 24/Baseline visit and the Week 52/Early Termination visit before other study procedures, such as blood draws and physical examinations, are performed.

6.6.1.8. Patient Diary

All women enrolled in the study will be provided with a patient paper diary, along with detailed instructions for its use. Patients will use the daily diary to record menstrual bleeding and use of feminine products. The diary will be reviewed by study staff at each visit.

6.6.2. Safety-Related Procedures

6.6.2.1. Weight

Patients should have weight measured while wearing indoor clothing and with shoes removed.

6.6.2.2. Vital Signs

Vital signs, including blood pressure, heart rate, and temperature, should be measured in the seated position after 5 minutes of rest and will include systolic and diastolic blood pressure and pulse rate.

6.6.2.3. Physical and Gynecologic Examinations

A complete physical examination will include head, ears, eyes, nose, mouth, thyroid, skin, heart and lung examinations, lymph nodes, gastrointestinal, skeletal, and neurological systems. All subsequent physical examinations should focus on signs and symptoms reported by the patient to assess for clinically significant changes from previous assessments.

6.6.2.4. Clinical Laboratory Samples

All protocol-required laboratory assessments must be conducted in accordance with the Study Reference Manual and the protocol Schedule of Activities (see Section 1.1). Laboratory requisition forms must be completed and samples must be clearly labelled with the Patient Identification Number, protocol number, site/center number, and visit date. Details for the preparation and shipment of samples will be provided. Reference ranges for all safety parameters will be provided to the site by the central laboratory. The samples collected for clinical laboratory tests are listed in [Table 4](#).

Table 4: Clinical Laboratory Tests

Chemistry	Hematology	Urinalysis
Potassium Chloride Bicarbonate Blood Urea Nitrogen Creatinine Glucose Calcium Phosphate Magnesium Sodium Albumin Creatinine Kinase Hemoglobin A1c Creatine Kinase Bilirubin Total Alanine Aminotransferase Aspartate Aminotransferase Gamma-Glutamyl Transferase Alkaline phosphatase	White Blood Cell (WBC) Count WBC Differential Red Blood Cell Count Hemoglobin Hematocrit Mean Corpuscular Volume Platelet Count RBC morphology	Protein Glucose Blood Urobilinogen Bilirubin Color and Clarity pH Leucocyte Esterase Ketones Nitrite Specific Gravity Urine Microscopy (reflex testing based on abnormal urine analysis)
	Lipids	Pregnancy
	Total Cholesterol Low Density Lipoprotein High Density Lipoprotein Triglycerides	Pregnancy test (human chorionic gonadotropin)
Hormones		
Estradiol		

The central laboratory will perform laboratory tests for chemistry, hematology, urinalysis, serology, and plasma and serum hormone levels. Each study site will conduct urine pregnancy tests locally.

All laboratory tests with values that are considered abnormal and clinically significant during participation in the study or within 28 days after the last dose of study drug should be repeated until the values return to normal, baseline, or have stabilized. Abnormal and clinically significant results should be reported as adverse events.

The investigator will maintain a copy of the reference ranges (with the record of the reference ranges) for the laboratory or laboratories used.

6.6.2.5. Electrocardiograms

ECGs (12-lead) will be obtained at Week 24 visit in the parent study and at the Week 52/Early Termination visit in this study, as well as if needed to evaluate any signs or symptom that require an ECG to assess. ECGs will be measured using standardized equipment provided by central core laboratory with the patient in a semi-supine or supine position after 5 minutes of rest. The ECGs will be assessed by central review and a report provided to the site. The investigator or sub-investigator (or a qualified individual at the investigational site) will interpret the ECG report provided by the central reviewer using one of the following categories: normal or abnormal. The investigator or sub-investigator will judge if any of the findings are clinically significant.

6.6.2.6. Bone Mineral Density

Bone mineral density is determined using DXA scanning and will be assessed at the lumbar spine (L1, L2, L3 and L4), total hip, and femoral neck (same leg within each patient). Training, quality review, and readings will be done by a central radiology laboratory as described in the central radiology charter for bone mineral density.

Throughout the study, the same DXA apparatus will be used at each site and operated in the same scan mode for all scans for an individual patient, and should be the same as used for the patient during the parent study (MVT-601-3001 or MVT-601-3002). A central core imaging laboratory will collect and evaluate all DXA scans for acceptability, and will have bone mineral density assessed as per the imaging charter. Data from the DXA scans will be managed and analyzed separately by the core laboratory and integrated into the study's database at the end of the study. Bone mineral density changes for individual subject will be monitored by a central radiology laboratory over the course of the study.

Patients who experience a bone mineral density loss from the parent study Baseline of $\geq 7\%$ at any of the anatomical sites assessed will be discontinued from the extension study. Patients should be assessed for secondary causes of bone loss if determined necessary by the investigator and followed up to resolution if bone mineral density loss is determined by the investigator to be related to study drug.

At Week 52 or an Early Termination visit occurring on or after Week 36, patients with a bone mineral density loss of $> 3\%$ at lumbar spine or total hip relative to parent study Baseline measurement will undergo another bone densitometry scan at 6 (± 1) months and will be contacted to obtain information about medications and conditions (eg, pregnancy) that might

affect bone mineral density through the time of the follow-up bone densitometry. If Early Termination occurs prior to Week 36, follow-up bone densitometry will be performed according to the requirements of the parent study. The follow-up bone densitometry will be submitted for central reading.

If the patient enrolls directly into another relugolix clinical study upon completion of the Week 52 visit, then the follow-up bone densitometry scan at 6 (\pm 1) months conducted under this protocol may be waived.

6.6.2.7. Status of Menstruation Recovery

If the first menstruation after the end of study treatment administration is observed before the Follow-up visit, the date of onset of the first menstruation is recorded in the electronic case report form (eCRF). Patients whose menses has not resumed as of the Follow-Up visit for whom there is no explanation for the lack of resumption (eg, medical procedure or medications) will be contacted again by telephone 3 (+ 0.5) months after the Follow-Up visit to determine if menses has resumed and will be asked about factors that may affect resumption of menses.

If the patient enrolls directly into another relugolix clinical study upon completion of the Week 52 visit, follow-up under this protocol to determine the status of menstruation recovery may not be required.

7. SAFETY CONSIDERATIONS

Study assessments of safety include adverse events, physical examinations, vital signs (and weight), ECGs, bone mineral density assessments, and clinical laboratory tests.

7.1. Adverse Event Definitions

7.1.1. Adverse Event

Adverse event: An adverse event is any unfavorable and unintended sign (including an abnormal laboratory finding), symptom, or disease (new or exacerbated) temporally associated with the use of a medicinal product, whether or not related to the medicinal product.

Events meeting the definition of an adverse event **include**:

- A worsening, excluding minor fluctuations, in the nature, severity, frequency, or duration of a pre-existing condition;
- Development of an intercurrent illness during the study;
- Development of symptoms that may or may not be related to the use of a concomitant medication or investigational product;
- Injury or accidents: If a medical condition is known to have caused the injury or accident, the medical condition and the accident should be reported as 2 separate medical events (eg, for a fall secondary to dizziness, both “dizziness” and “fall” should be recorded separately); and
- An investigational abnormality (eg, laboratory parameter, vital sign, ECG) only if the abnormality is considered clinically significant by the investigator based on at least one of the following criteria:
 - Induces clinical signs or symptoms;
 - Requires active intervention;
 - Requires interruption or discontinuation of study drug.

Events that **do not** meet the definition of an adverse event include:

- Medical or surgical procedures (eg, surgery, endoscopy, tooth extraction, transfusion); the condition that leads to the procedure is an adverse event;
- Pre-existing diseases or conditions present or detected before the start of study drug administration that do not worsen;
- Situations where an untoward medical event has not occurred (eg, planned hospitalization for an elective procedure, with elective defined as known or planned at the time of signing of the informed consent);
- Events of heavy menstrual bleeding, as heavy menstrual bleeding is quantified as an efficacy endpoint, unless meets seriousness criteria.

Adverse events that occur during the study should be evaluated by the investigator and graded according to Common Terminology Criteria for Adverse Events (CTCAE). Episodic adverse

events, such as vomiting, or those that occur repeatedly over a period of consecutive days are “intermittent”. All other events are “continuous”. Additional information on detecting, documenting, and reporting adverse events and serious adverse events are provided below. No toxicity-related dose reductions of study drug are permitted, however, study drug can be held for a period of up to 2 weeks for evaluation and treatment of an adverse event. The study drug may be restarted if deemed safe for the patient by the investigator.

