4.5. Removal of Patients from Therapy

Completion of the Week 52 visit defines completion of the study. Patients may withdraw consent to participate in the study and discontinue treatment at any time for any reason. Investigators or the medical monitor may remove patients from therapy under this protocol for reasons of safety and/or lack of compliance as discussed below. Patients removed from therapy for any reason will undergo the assessments for the Early Termination visit (see the Week 52 visit on the Schedule of Activities, Section 1.1) and will have a Follow-up visit to assess safety approximately 30 days after the end of study drug treatment (ie, after the patient's last dose of study medication).

The following safety and/or compliance events will result in the removal of patients from therapy either permanently or until the etiology of the problem has been identified and resolved:

- Any adverse event that is intolerable to the patient and that cannot be ameliorated by the use of adequate medical intervention, or that in the opinion of the investigator or medical monitor would lead to undue risk to the patient if dosing continued;
- If it is discovered after enrollment that a patient failed to meet protocol entry criteria and continued participation poses an unacceptable risk to the patient's health;
- If the following liver test abnormalities develop, study drug should be discontinued immediately with appropriate clinical follow-up (including repeat laboratory tests, until a patient's laboratory profile has returned to normal/baseline status):
 - ALT or AST > 8 x ULN; or
 - ALT or AST > 5 x ULN and persists for more than 2 weeks; or
 - ALT or AST > 3 x ULN in conjunction with elevated total bilirubin > 2 x ULN or international normalized ratio (INR) > 1.5; or
 - ALT or AST > 3 x ULN with appearance of fatigue, nausea, vomiting, right upper quadrant pain or tenderness, fever, rash and/or eosinophilia (> 5%);
- QT interval by the Fridericia correction (QTcF) prolongation of more than 500 msec read by a cardiologist;

-
- Evidence of endometrial hyperplasia or endometrial carcinoma on endometrial biopsy;
 - If the patient has a $\geq 7\%$ loss of bone mineral density at lumbar spine, total hip, or femoral neck compared with the parent study Baseline;

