5.5. Dose Reduction/Dose Administration

No toxicity-related dose reductions of study drug are permitted. Patients who experience a grade 3 or greater toxicity that cannot be ameliorated by the use of adequate medical intervention should have their treatment interrupted until the toxicity improves to a grade 2 or lower severity. Study drug can be held for a period of up to 2 weeks for evaluation and treatment of an adverse event. Patients may subsequently be re-started on study drug with the written approval of the sponsor (or designee).

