7.5. Adverse Events of Clinical Interest Reporting

Adverse events of clinical interest in this study are defined as any increase in ALT or AST $\geq 3 \times$ ULN.

Any ALT or AST elevation of this degree or greater occurring during the Open-Label Treatment period or Follow-up period should be reported to the sponsor using the Serious Adverse Event Form **within 24 hours of the study site personnel's knowledge of the event** (see Section 7.6), **even if the event does not meet serious adverse event criteria**. Additional instructions for evaluating patients with an increase in ALT or AST $\geq 3 \times$ ULN may be found in [Appendix 3](#).

7.5.1. Criteria for Temporary Withholding of Study Drug in Association with Liver Test Abnormalities

Hepatic enzymes will be monitored in accordance with FDA drug-induced liver injury guidelines [[FDA, 2009](#)].

If the following liver test abnormalities develop, study drug should be withheld immediately with appropriate clinical follow-up (including repeat laboratory tests, until a patient's laboratory profile has returned to normal/baseline status), and the event reported as a serious adverse event:

- ALT or AST $> 8 \times$ ULN; or
- ALT or AST $> 5 \times$ ULN and persists for more than 2 weeks; or
- ALT or AST $> 3 \times$ ULN **and** total bilirubin $> 2 \times$ ULN **or** INR > 1.5 ; or
- ALT or AST $> 3 \times$ ULN with appearance of fatigue, nausea, vomiting, right upper quadrant pain or tenderness, fever, rash and/or eosinophilia ($> 5\%$).

Rechallenge may be considered if an alternative cause for the abnormal liver tests (ALT, AST, total bilirubin) is discovered and the laboratory abnormalities resolve to normal or Week 24/Baseline values. The investigator and sponsor must discuss and agree with any decision to rechallenge.

Rechallenge should not occur when the etiology of the liver test abnormalities is considered possibly drug induced.

7.5.2. Criteria for Permanent Discontinuation of Study Drug in Association with Liver Test Abnormalities

Study drug treatment should be discontinued permanently if all of the following 4 criteria are met (ie, potential severe drug-induced liver injury/Hy's law case):

1. AST or ALT increases to ≥ 3 x ULN; AND
2. Total bilirubin increases to > 2 x ULN or INR > 1.5 ; AND
3. Alkaline phosphatase value does not reach 2 x ULN; AND

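### Protocol 7.1.1 lets study drug be restarted on the investigator's judgement alone, without the grade check and written sponsor approval that 5.5 requires after severe toxicity

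*Protocol*

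**What the plan says.** Section 5.5 (Dose Reduction/Dose Administration) opens with severe toxicity, meaning grade 3 or above that medical treatment has failed to ameliorate. The rule for these patients is that they "should have their treatment interrupted until the toxicity improves to a grade 2 or lower severity". It then allows a hold without naming a grade: "Study drug can be held for a period of up to 2 weeks for evaluation and treatment of an adverse event". The restart rule follows directly: "Patients may subsequently be re-started on study drug with the written approval of the sponsor (or designee".

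Section 7.1.1 (Adverse Event) ends with the same subject. It repeats that toxicity-related dose reductions are not allowed, describes the same hold ("study drug can be held for a period of up to 2 weeks for evaluation and treatment of an adverse event"), and closes with its own restart rule: "The study drug may be restarted if deemed safe for the patient by the investigator".

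Two other sections bear on restarting. Section 4.5 lists events that lead to "removal of patients from therapy either permanently or until the etiology of the problem has been identified and resolved", but names nobody who must approve a return to treatment. Section 7.5.1 covers liver test abnormalities only, and there the rule is explicit: "The investigator and sponsor must discuss and agree with any decision to rechallenge".

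**The concern.** Two sections authorise the same interruption and then differ on who decides that it ends and on what basis. In 5.5 the sponsor must approve in writing and, after severe toxicity that could not be ameliorated, the grade must first have fallen. In 7.1.1 the investigator's view that restarting is safe appears to be enough.

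What is at stake is patient safety on re-exposure. Site staff handling an adverse event are likely to consult the adverse-event section. If they follow 7.1.1 as written, they could restart drug after a severe toxicity without checking for grade 2 or lower and without the sponsor's written approval. Monitors would also have two texts against which to judge the same restart. The protocol plans approximately 240 sites (Synopsis), so consistent practice depends on the text being clear.

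**Working it through.** There is no figure to reproduce; the check is a comparison of text.

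**1. Do both sections describe the same hold?** Yes. Apart from the opening capital, the hold sentence is the same run of 21 words in both, and each section also rules out toxicity-related dose reduction.

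**2. Does 7.1.1 reach severe events?** Yes. It sets no grade limit, and the paragraph containing the restart sentence begins by requiring adverse events to be graded by CTCAE. It cannot be read as a rule for low-grade events only.

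**3. Which restart conditions appear where?** For non-liver toxicity of grade 3 or greater that cannot be ameliorated:

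| Condition | Section 5.5 | Section 7.1.1 |
|---|---|---|
| Improvement to grade 2 or lower | Required | Not stated |
| Written approval of sponsor or designee | Required | Not stated |
| Investigator judges restart safe | Not stated | Only condition given |
| Reference to the other section | None | None |

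Section 7.1.1 therefore states 0 of the 2 conditions in 5.5.

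**4. What about other non-liver adverse-event holds?** Section 5.5 does not say whether written approval extends to them.
- Narrower reading: its paragraph starts with grade 3 or greater toxicity, so approval belongs to those events. Section 7.1.1 then omits nothing for lower-grade holds.
- Wider reading: the approval sentence directly follows a hold sentence that has no grade limit, so approval covers every adverse-event hold. Section 7.1.1 then omits 1 condition for the lower-grade holds as well. This is probably the more natural reading.

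The mismatch for severe toxicity is present on both readings.

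**5. Does another section reconcile the two?** No.
- Section 4.5 provides for temporary removal but names no restart approver.
- Section 7.5.1 requires agreement between investigator and sponsor, but only for liver tests, so liver holds fall outside this point.
- Table 3 in Section 5.9.1 requires medical monitor approval to hold drug for a short course of a P-glycoprotein inducer, which concerns concomitant medication and not restart after toxicity.

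In 5.5, 7.5.1 and Table 3 the protocol keeps oversight outside the site. Section 7.1.1 is the exception, which suggests a drafting gap and not deliberate delegation.

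**6. Is this the current text?** Yes. The superseded protocol version in the same file has the same two rules, so the amendment did not introduce the mismatch.

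**The case against.** The strongest reply is that nothing conflicts. Section 7.1.1 sits under definitions and gives a short restatement of the hold; 5.5 is the operative dosing section. The wording in 7.1.1 is permissive and waives nothing. Section 10.1.10 makes the investigator responsible for following the procedures in the protocol, so 5.5 binds whatever 7.1.1 leaves out. Section 4.5 also requires removal after an intolerable adverse event that cannot be ameliorated, or one posing undue risk, either permanently or until the cause is found and resolved. Serious events are reported within 24 hours (7.6), and monitors verify adherence (8.2). On this view the point is a missing cross-reference.

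Much of this stands. The rules can be met together, a site restarting on 7.1.1 alone would be departing from 5.5, and 4.5 independently constrains restart for some of these patients. It does not reconcile the text, however. A sentence saying drug may be restarted if one condition is met is naturally read as making that condition sufficient. Section 4.5 supplies no approver and may not reach every grade 3 event. Reporting and monitoring, like the SAP's tabulation of adverse events leading to dose interruption (9.1 and 9.1.5), do not set the conditions for restart.

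**Conclusion.** The point holds as a minor inconsistency in a patient-safety procedure that should be corrected. On every reading it affects non-liver holds for toxicity of grade 3 or greater that cannot be ameliorated, where 7.1.1 omits both conditions in 5.5. If approval in 5.5 covers all adverse-event holds, it also affects the remaining non-liver holds, where 7.1.1 omits the approval. The documents do not give the number of holds, so no frequency or extent of harm can be stated. Efficacy and safety analyses are not affected. The conclusion rests on the wording of the current protocol and on reading the restart sentence in 7.1.1 as complete in itself, which is how a site would probably take it.

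**What to change.** Amend the last sentence of 7.1.1 so that restart requires both the investigator's judgement of safety and compliance with the restart conditions in Section 5.5, or in Section 7.5.1 for liver test abnormalities. While the text is open, it would be helpful, though secondary, to state in 5.5 whether written sponsor approval applies to every adverse-event hold or only to toxicity of grade 3 or greater.

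The cost is one amended sentence, plus one scope statement if the second change is made. Data collection and analysis stay as they are. Some restarts may be delayed briefly while approval is obtained, and there would be more approvals to process if the sponsor chooses the wider scope.
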